11.1.2 Anthropometrics

Body mass index (BMI), height, and weight

Body weight and standing height were measured at the assessment centre visit at recruitment. BMI was calculated as a participant’s body weight (kg) divided by the square of their height (m).

Other body composition measures

Bioimpedance was measured at the assessment centre visit at recruitment using the Tanita Bc418ma bioimpedance device, from which body fat percentage, whole-body fat mass, whole-body fat-free mass were estimated. Hand grip strength (for each hand) was measured using the Jamar Hydraulic hand dynamometer. Left calcaneal bone mineral density (BMD) was measured using a Norland McCue Contact Ultrasound Bone Analyzer, from which a heel BMD t-score was calculated for each participant. At the second instant of follow-up (2014), a dual energy X-ray absorptiometry (DXA) scan was used to measure left femoral neck BMD (from which femoral neck BMD t-scores were calculated), and total bone mineral content (BMC).

11.1.3 Lifestyle

Physical activity

Physical activity in total metabolic equivalent task (MET) minutes per week was calculated based on a series of questions that asked about frequency and duration of walking, moderate activity, and vigorous activity, and will be used in this study.

Smoking status

At recruitment, participants were asked in the touchscreen questionnaire “Do you smoke tobacco now?” and “In the past, how often have you smoked tobacco?” to determine their smoking status as current, previous, never, or unknown.

Alcohol consumption

In the touchscreen questionnaire at recruitment, participants were asked about their weekly and monthly intake of glasses of red wine, glasses of champagne plus white wine, pints of beer plus cider, measures of spirits or liqueurs, glasses of fortified wine, and glasses of other alcohol. We will sum participants weekly and monthly alcohol intakes, respectively. Weekly-based total alcohol intakes will be converted into daily total alcohol intake (drinks/day). For those with missing weekly-based alcohol intakes for any specific type, monthly-based intakes will be used.

Participants with missing data for weekly and monthly intake of specific alcohol types will be considered non-consumers. Non-consumers of total alcohol intake (drinks/day) will be cross-checked with responses to a question in the touchscreen questionnaire at recruitment that asked “how often do you drink alcohol?” with options of 1 “daily or almost daily”, 2 “three or four times a week”, 3 “once or twice a week”, 4 “one to three times a month”, 5 “special occasions only”, 6 “never”, or 7 “prefer not to answer”.

Diet and nutrition

Alternative Healthy Eating Index Score, energy intake, and nutrient intakes

The Alternative Healthy Eating Index (AHEI) will be used as an index of diet quality. Adherence to the AHEI has previously been inversely associated with risk of hip fracture, and could plausibly vary by diet group (8).

The AHEI awards between 0-10 points for 11 food and nutrient components. Points are awarded for 1) higher intakes of vegetables, whole fruits, nuts and legumes, wholegrains, polyunsaturated fatty acids, and n-3 fatty acids; 2) lower intakes of red and processed meats, sugar-sweetened beverages and fruit juices, trans fats, and sodium; and 3) moderate intake of alcohol. The total possible score ranges from 0-110 points. Table S1 shows how each food or nutrient component will be calculated and scored (9).

Component	Criteria for minimum score (0)	Criteria for maximum score (0)	Component derivation
Vegetables, servings/day	0	≥ 5	Participants were asked in the touchscreen questionnaire at recruitment how many heaped tablespoons of cooked vegetables and raw vegetables/salad they ate per day, respectively. These will be summed to give total vegetable intake, and two heaped

			tablespoons will be considered as one serving of vegetable intake.
Fruit, servings/day	0	≥ 4	Participants were asked in the touchscreen questionnaire at recruitment how many pieces of fresh fruit and dried fruit they ate per day, respectively. These will be summed to give total fruit intake. One piece of fresh fruit and two pieces of dried fruit will each be considered a serving of fruit, respectively.
Wholegrains, g/day			Intake of wholegrains (g/day) has been previously calculated using 24-hour dietary recall data, and will be used in this study.
Women		75	
Men		90	
Sugar-sweetened beverages and fruit juice, servings/day	≥ 1	0	Intake of sugar-sweetened beverages and fruit juice (both in g/day) have been previously calculated using 24-hour dietary recall data. Each will be divided by standard portion sizes, then will be summed to give total intake of sugar-sweetened beverages and fruit juice (servings/day)
Nuts and legumes, servings/day	0	≥ 1	Intakes of legumes and pulses, salted nuts and seeds, and unsalted nuts and seeds (each in g/day) have been previously calculated using 24-hour dietary recall data. Each will be divided by standard portion sizes, then will be summed to give nuts and legumes intake (servings/day).
Red/processed meat, servings/day	≥ 1.5	0	Participants were asked in the touchscreen questionnaire at recruitment how often they ate processed meat, beef, lamb/mutton, and pork, respectively. Responses to these questions will be converted to daily-based consumption frequencies, and will be summed

			to give total red and processed meat intake in servings per day
Trans fat, % of energy	≥ 4	≤ 0.5	Trans fat intake (g/day) and total energy intake (kJ/day) have been previously estimated using 24-hour dietary recall data. We will calculate trans fat (% energy) using these two s, and conversion rates of 1 kJ = 4.184 kcal and 1 g trans fat = 9 kcal, respectively.
omega-3 fats (EPA +DHA), mg/day	0	250	Omega-3 fatty acid intake (g/day) has been previously estimated using 24-hour dietary recall data.
PUFA, % of energy	≤ 2	≥ 10	PUFA intake (g/day) and total energy intake (kJ/day) have been previously estimated from 24-hour dietary recall data. We will calculate PUFA (% energy) using these two s, and conversion rates of 1 kJ = 4.184 kcal and 1 g PUFA = 9 kcal, respectively.
Sodium, mg/day	Highest decile	Lowest decile	Previously estimated using 24-hour dietary recall data (mg/day).
Alcohol (drinks/day)			
Women	≥ 2.5	0.5 – 1.5	
Men	≥ 3.5	0.5 – 2.0	
Total	0	110	Sum each individual component score per participant.

Scoring based on available guidelines for calculating Alternative Healthy Eating Index Score (9), and dietary nutrient intakes based on previous calculations from 24-hour dietary recall data (10).

Where possible, we will use dietary data collected from the touchscreen questionnaire to estimate food intakes. Total energy intake and dietary nutrient intakes, including protein, calcium, and omega-3 fatty acid intakes, were previously calculated from 24-hour dietary recall data, and will be used in this study (10).

Circulating vitamin D and insulin-like growth factor 1 (IGF-1) levels

Circulating IGF-1 and vitamin D levels (both in nmol/L) were measured by CLIA analysis on a DiaSorin Ltd LIASON XL.

Use of nutritional supplements

At recruitment, participants were asked in the touchscreen questionnaire if they regularly take any of the following supplements: vitamin A, vitamin B, vitamin C, vitamin D, vitamin E, folic acid or folate (vitamin B9), multivitamins or minerals, none of the above, or prefer not to answer. From this, we will define the variable “use of nutritional supplements” with options of yes, no, or unknown.

In the online 24-hour recall assessment of diet, participants were also asked “Did you have any vitamin or mineral supplements yesterday”, with more detailed options available. We will regroup responses to this question into the following supplementation categories: “Calcium”, “Vitamin D”, “Fish oil”, “Vitamin B12”, “Multivitamin”, “Other”, or “None”, or “Unknown”.

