8.1.3 Accounting for confounding

Unadjusted and adjusted cox models will be applied. Both will control for age by using attained age as the timescale. The adjustment set for the adjusted model will be informed by a DAG model, which will be constructed using the online tool DAGitty, following available guidelines on their use (3). Confounders will be considered as covariates that are 1) risk factors of the outcome; 2) associated with the exposure; and 3) not on the causal pathway (4). Potential confounders are age at recruitment, sex, region, ethnicity, socio-economic status or education, marriage, physical activity, smoking, alcohol, BMI (or height and weight), number of children, menopausal status, hormone replacement therapy (HRT) in postmenopausal women, chronic disease prevalence at recruitment, and use of nutritional supplements (either generic or supplement-specific e.g. for calcium, vitamin D, and fish oil in particular, depending on availability of data). A list of likely confounders and their derivation is summarised in Supplementary Table 1.

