11.1.4 Other

Number of children

At recruitment in the touchscreen questionnaire, women were asked “how many children have you given birth to?”. This will be treated as a continuous variable. This variable is not applicable to men.

Menopausal status

At recruitment in the touchscreen questionnaire, women were asked multiple questions relating to menopausal status. Women will be defined as premenopausal or postmenopausal at recruitment using the following criteria:

Premenopausal: answered “no” to the question that asked about having gone through menopause, or answered “not sure”, and:

- Were < 55 years old, did not report having a bilateral oophorectomy or hysterectomy, and did not report using hormone replacement therapy (HRT), or
- Were < 55 years old, did not report having a bilateral oophorectomy or hysterectomy, and reported menstruating on the day of recruitment

Postmenopausal: answered “yes” to having gone through menopause, or answered “not sure” and were ≥ 55 years old or had a bilateral oophorectomy.

Menopausal hormone replacement therapy (HRT)

At recruitment in the touchscreen questionnaire, women were asked “Have you ever used hormone replacement therapy?” and if yes, “How old were you when you last used hormone replacement therapy?”. We will categorise HRT use based on these questions as “Current”, “Former”, “Never”, or “Unknown”.

Chronic disease prevalence at recruitment

We will identify prevalence of chronic diseases that could act as confounders using both self-reported information from questions on health and medical history asked in the touchscreen questionnaire, and through use of hospital records (with the date of diagnosis being before or on the date of recruitment). Relevant chronic diseases that will be considered confounders will be informed by existing literature and by use of a Directed Acyclic Graph (DAG), but will likely include hip fracture, other fracture, osteoporosis, diabetes, cardiovascular disease, and cancer.

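### Past smoking is asked by frequency but the covariate keeps only status, so some smoking confounding may stay in the diet-group hazard ratios, and no sensitivity analysis checks this

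*SAP*

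**What the plan says.** SAP 11.1.3 (Smoking status) names two touchscreen questions. One asks whether the participant smokes now. The other is "In the past, how often have you smoked tobacco". Together they serve "to determine their smoking status as current, previous, never, or unknown". The answer options are not listed for either question, and no rule says which past-frequency answers count as previous and which as never.

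SAP 8.1.3 puts smoking among the potential confounders ("physical activity, smoking, alcohol, BMI (or height and weight), number of children, menopausal status") without giving its form. It adds: "The adjustment set for the adjusted model will be informed by a DAG model". A DAG decides which variables enter the model, not how finely each is coded.

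Other lifestyle covariates in 11.1.3 are kept as quantities. For alcohol, "Weekly-based total alcohol intakes will be converted into daily total alcohol intake (drinks/day", and physical activity is in MET-minutes per week. The six items in 8.4 do not vary the smoking variable.

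**The concern.** A frequency answer is collected and then not used beyond sorting people into status levels. A level such as previous can then hold people with very different exposure. Adjusting for status removes the confounding that comes from different proportions of current, previous and never smokers. It does not remove confounding that comes from different intensity within those levels.

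Two conditions must hold for this to bias the primary hazard ratios: intensity within a level differs by diet group, and intensity affects hip fracture. If both hold and lower-meat groups smoke less heavily, their hazard ratios are pulled downwards and an excess hip-fracture risk would be partly hidden. SAP 8.3 makes the mediation analysis conditional on a significant main result, so a hidden association would stop that analysis too. As planned, a reader could not see whether the coding matters.

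**Working it through.** **1. Benchmark from the SAP.** Section 6.0 gives no figure for smoking; the nearest yardstick is Table 3. For vegetarians against regular meat-eaters:
- p = 8,685 / (8,685 + 247,571) = 0.0339
- SD = √[p(1 − p)] = 0.181
- events = 0.03 × 256,256 = 7,688
- SE of log HR = 1 / (0.181 × √7,688) = 0.063
- minimum detectable HR = exp[(1.960 + 0.842) × 0.063] = 1.19, as stated.

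The same steps give 1.17 for pescatarians and 1.05 for occasional meat-eaters, also as stated.

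**2. Inputs for the residual bias (all assumed; the SAP gives none).** True diet HR = 1.00. Previous and current smokers: 36% and 12% of regular meat-eaters, 33% and 7% of vegetarians. HR against never smokers: previous light 1.1, previous heavy 1.3–1.5, current light 1.3–1.5, current heavy 1.8–2.5. The heavy share h among smokers is varied.

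**3. Formulas.** For group g, with previous and current proportions p and c, let P and C be the average HR in previous and current smokers: (1 − h) × light + h × heavy. Average risk R = 1 − p − c + pP + cC. Subscripts v and r are vegetarian and regular.
- Unadjusted factor = R_v / R_r
- Factor left after status-only adjustment = R_v / E, where E = 1 − p_v − c_v + p_v·P_r + c_v·C_r
- Share left = ln(adjusted) / ln(unadjusted)

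**4. Largest case.** Heavy share 60% against 30%; previous 1.1/1.5; current 1.3/2.5.
- P_r = 0.4 × 1.1 + 0.6 × 1.5 = 1.34; P_v = 0.7 × 1.1 + 0.3 × 1.5 = 1.22
- C_r = 0.4 × 1.3 + 0.6 × 2.5 = 2.02; C_v = 0.7 × 1.3 + 0.3 × 2.5 = 1.66
- R_r = 0.52 + 0.36 × 1.34 + 0.12 × 2.02 = 1.2448
- R_v = 0.60 + 0.33 × 1.22 + 0.07 × 1.66 = 1.1188
- E = 0.60 + 0.33 × 1.34 + 0.07 × 2.02 = 1.1836
- Unadjusted 0.899; adjusted 1.1188 / 1.1836 = 0.945; share left 53%

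**5. Range over the assumed HRs.**

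| Heavy share, regular / vegetarian | Unadjusted | After status-only adjustment | Share left |
|---|---|---|---|
| 50% / 50% | 0.952–0.971 | 1.000 | 0% |
| 50% / 40% | 0.936–0.962 | 0.981–0.991 | 20–32% |
| 60% / 40% | 0.916–0.951 | 0.964–0.982 | 31–46% |
| 60% / 30% | 0.899–0.942 | 0.945–0.973 | 41–56% |
| 40% / 50% (reversed) | 0.969–0.986 | 1.009–1.019 | direction reversed |

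If vegetarians are instead given the same status split as regular meat-eaters (36% and 12%), the lower end for 60% / 30% is 0.931. That case removes any difference in smoking status, so it is a stress test rather than the main range.

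**6. Second calculation with other inputs.** A Poisson fit to expected counts for 247,571 and 8,685 people, true diet HR 1.00, adjusted for three-level status. Past smokers 36% in both groups, current 11% and 7%. HRs: light past 1.0, daily past 1.2–1.3, light current 1.2–1.3, daily current 1.6–2.0.
- Daily shares differing by 10–25 points: 0.965–0.991
- Equal shares (65% past, 80% current): 1.000
- Five points lower in vegetarians (65 / 60% and 80 / 75%): 0.993–0.995
- Five points higher in vegetarians: 1.005–1.007

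**7. Effect on inference for vegetarians.** For a true HR of 1.19, power is 80%. A factor of 0.965 shifts the test statistic by ln(0.965) / 0.063 = −0.57 and lowers power to about 61%; 0.991 lowers it to about 76%.

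**8. If only past smoking can be split.** In the case of step 4, E becomes 0.60 + 0.33 × 1.22 + 0.07 × 2.02 = 1.1440 and the factor is 1.1188 / 1.1440 = 0.978 instead of 0.945. This assumes that reported frequency captures the heavy/light distinction.

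**The case against.** The strongest reply is that nothing here is wrong on the SAP's own terms. Status is a clear definition, no passage contradicts it, and other covariates are coarse too (three regions, living alone yes/no). That stands: this is a choice that can be improved, not an error.

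A reader might infer that a sizeable bias remains and that it always makes lower-meat groups look safer. The document does not support this. It holds no data on smoking intensity by diet group. With equal intensity the residual is nil, with a five-point difference it is under 1%, and a reversed difference turns the direction round. The share left also depends on the inputs: in step 6, lowering past smoking in vegetarians from 36% to 30% reduces it from about 32–54% to 24–43%. Other listed covariates, such as deprivation and alcohol, could absorb part of what remains.

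A reader might also infer that both questions record frequency, or that rare past smokers are certainly coded as previous. Only the past question is shown to ask frequency, and the mapping is not written down. Reported frequency is not amount, duration or time since quitting, so splitting by it may remove only part of the residual.

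What survives is narrower. Past frequency is asked, the levels do not keep it, and no planned analysis shows whether that matters.

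**Conclusion.** The point holds in conditional form. Past smokers of different frequency can share one covariate level, and the plan has no check on the consequence. Under the assumed inputs, status-only adjustment multiplies the vegetarian HR by about 0.95 to 1.00. It leaves none of the smoking confounding if intensity within levels is the same across diet groups, and up to about half in the largest cases.

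The bias is smaller than the minimum detectable effect for vegetarians (1.19; reciprocal 0.84). It would be tempting to set it against the 1.05 for occasional meat-eaters, but that group's smoking contrast was not modelled and may be smaller, so no such comparison is made.

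HRT shows a similar reduction: 11.1.4 asks "How old were you when you last used hormone replacement therapy" and forms current, former and never categories. That answer may be needed to separate current from former use, and no size or direction of bias has been shown. It does not carry the point.

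**What to change.** In 11.1.3:
- split previous smokers by reported past frequency;
- state which past-frequency answers count as previous and which as never, in particular where infrequent past smokers go;
- split current smokers by frequency or amount if this was recorded at recruitment;
- keep an unknown level.

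Use this variable in the adjusted model of 8.1.3 and keep the three-level status for the descriptive tables. Reporting the adjusted hazard ratios under both codings would show whether the coding matters.

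For past smoking, no new data collection is needed. The cost is a change of wording, a few extra degrees of freedom, and slightly more unknown values where frequency was not answered. Splitting former HRT use by time since last use is optional.

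### The alcohol variable sums glasses, pints and measures without weights and calls the total drinks/day, so it measures alcohol dose with an error that depends on beverage type

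*SAP*

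**What the plan says.** Under Alcohol consumption in SAP section 11.1.3, intake is recorded in mixed containers: "glasses of red wine, glasses of champagne plus white wine, pints of beer plus cider, measures of spirits or liqueurs, glasses of fortified wine", plus glasses of other alcohol. The aggregation rule follows, and the step after it is a change of time scale only: "We will sum participants weekly and monthly alcohol intakes, respectively. Weekly-based total alcohol intakes will be converted into daily total alcohol intake (drinks/day". Monthly answers serve as a fallback: "For those with missing weekly-based alcohol intakes for any specific type, monthly-based intakes will be used". Where both are missing, the person is treated as a non-consumer of that type, and non-consumers of alcohol overall are cross-checked against a frequency question.

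The AHEI component table in the same section has a row headed "Alcohol (drinks/day" and closing bracket. Its cut-points are 0.5-1.5 for the full score and 2.5 or more for zero in women, and 0.5-2.0 and 3.5 or more in men. The derivation cell for alcohol is blank in the text at hand.

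Alcohol is listed among the potential confounders in section 8.1.3. The AHEI is a potential effect modifier (sections 1.2 and 8.2), used as a median split and per five units.

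**The concern.** Followed as written, the rule adds containers first and rescales time afterwards. Once the types have been added together, no beverage-specific weight can be applied, so a pint of beer and a measure of spirits each add one drink. The AHEI cut-points are then applied to that count.

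Other rows of the table handle mixed units differently. Two heaped tablespoons make one vegetable serving, two pieces of dried fruit count as one piece of fresh fruit, and nuts, legumes and sweet drinks are divided by standard portion sizes. The fruit row is the nearest parallel, because it also combines unlike units from the touchscreen questionnaire, and there the weights are stated.

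Two things are at stake: how well the adjusted model controls for alcohol, and whether participants get the right alcohol component in the AHEI. The error follows beverage type, so it is not purely random. If beverage choice differs between diet groups, some residual confounding could remain, but the SAP contains no data on that.

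**Working it through.** The SAP has no figure that depends on this derivation, so there is nothing to reproduce. The check is whether the choice of weight matters at the SAP's own cut-points.

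**Inputs**
- From the SAP: the container list, the sum, and the cut-points for men (full score 0.5-2.0, zero at 3.5 or more).
- Assumed, because the SAP gives none: beer 3.5-5% in a 568 mL pint; spirits 37.5-40% in a 25 mL measure; ethanol 0.789 g/mL; a reference drink of 10, 12 or 14 g; a straight-line score between the cut-points.

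**Alcohol per container** (mL x strength x 0.789)
- Pint: 568 x 0.035 x 0.789 = 15.7 g, to 568 x 0.05 x 0.789 = 22.4 g.
- Measure: 25 x 0.375 x 0.789 = 7.4 g, to 25 x 0.40 x 0.789 = 7.9 g.
- Ratio: 15.7/7.9 = 2.0, to 22.4/7.4 = 3.0. This does not depend on the reference drink size.

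**AHEI alcohol score in men**, 10 x (3.5 - x)/1.5 for x between 2.0 and 3.5 drinks/day

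| Intake | Unweighted | Reference drink 14 g | 12 g | 10 g |
|---|---|---|---|---|
| 2 pints/day at 18 g (36 g) | 2.0, score 10 | 2.57, score 6.2 | 3.0, score 3.3 | 3.6, score 0 |
| 3.5 measures/day at 8 g (28 g) | 3.5, score 0 | 2.0, score 10 | 2.33, score 7.8 | 2.8, score 4.7 |

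Over the whole assumed range for a pint, 2 pints/day runs from 2 x 15.7/14 = 2.24 drinks (score 10 x (3.5 - 2.24)/1.5 = 8.4) to 2 x 22.4/10 = 4.48 drinks (score 0). The error for that man is therefore 1.6 to 10 points, depending on the assumptions.

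**Away from the cut-points** (18 g per pint, 8 g per measure)
- 1 pint/day: 18/14 = 1.3 to 18/10 = 1.8 drinks.
- 1 measure/day: 8/14 = 0.57 to 8/10 = 0.8 drinks.
- 2 measures/day: 16/14 = 1.1 to 16/10 = 1.6 drinks.

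All of these lie within 0.5-2.0 and score 10 with or without weighting. The misscoring is therefore confined to intakes near a cut-point.

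**Monthly fallback**
- 8 drinks/month divided by 30.44 is 0.26/day, below the 0.5 lower bound of the full-score band.
- If the same count were placed in a weekly total and divided by 7, it would be 1.14/day, inside that band for both sexes. The inflation would be 30.44/7 = 4.35-fold.
- The SAP does not say that this will be done.

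**The case against.** The strongest reply is that equal weighting is inferred. Nowhere does the SAP say that a pint equals a measure, and the blank table cell could be filled sensibly by the analyst. That is fair as to intent. Still, an unweighted sum is what the text yields if followed, and no weights appear anywhere in the document.

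A second reply is that counting occasions as servings is a habit of this SAP: the meat and fish questions, and the red and processed meat row, are also summed unweighted. This stands as context. It does not remove the known difference in alcohol between a pint and a measure.

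Third, the table's examples sit exactly on cut-points, the straight-line score is assumed, and the drink size in the cited scoring guideline cannot be seen here. All of this stands. Errors of several points are therefore illustrations for selected individuals and do not describe a typical participant.

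A reader might go further and infer two things that the document does not support. One is that the variable fails to measure alcohol dose at all; a drink count is an imprecise proxy, and for many intakes the AHEI score is unaffected. The other is that monthly counts will enter about four times too high. The SAP sums weekly and monthly answers separately and names the target unit, so an analyst would ordinarily divide by days per month. The missing divisor is a gap in wording, just as the divisor of 7 for weekly counts is left unstated.

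**Conclusion.** The point holds in a limited form. As written, the derivation is a container count labelled drinks/day, and it carries a beverage-dependent error. A pint holds about 2 to 3 times the alcohol of a spirit measure under the assumed strengths and volumes, yet both count as one. Some participants near the AHEI alcohol cut-points would be scored wrongly; how many is unknown.

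The consequence is bounded. Alcohol is one of many potential confounders, in a set still to be settled by a DAG. In the AHEI it carries 10 of 110 points (9.1% of the range) of a secondary effect modifier. The effect on any hazard ratio, or on the number of people crossing the AHEI median, cannot be worked out from the SAP. The point is worth acting on because the remedy is cheap and uses data already in the plan.

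**What to change.** In section 11.1.3, change the order of the steps:
1. For each beverage type, convert the count to a daily amount (weekly count divided by 7; monthly count divided by 30.4 where the weekly answer is missing), and say that this substitution is made type by type.
2. Multiply each daily count by a stated average alcohol content for that container, including one for the glasses of other alcohol.
3. Sum to g/day and use this as the alcohol covariate.
4. For the AHEI, divide g/day by one stated reference drink size consistent with the cited scoring guideline, and record this in the alcohol row of the component table.

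The cost is a few lines of SAP text and code, with no new data. The drawback is that the alcohol contents are assumed averages and will not fit every drink. Writing down the monthly divisor in step 1 is a clarification only.

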1.2 Secondary objectives

- To determine the roles of potential modifying factors on associations between each diet group and hip fracture risk, including age, sex, body mass index (BMI), and adherence to the Alternative Healthy Eating Index (AHEI).
- To investigate interactions between diet groups and genotypes on bone mineral density (BMD) and hip fracture risk.
- To determine the roles of potential mediating factors on any observed associations between diet groups and hip fracture risk, including the roles of BMI, measures of body composition measures, circulating levels of vitamin D and IGF-1, and dietary intake of protein, calcium, vitamin B12, and omega-3 fatty acids.

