8.2 Subgroup analyses

We will stratify the adjusted model by potential effect modifiers, and will add these covariates to adjusted models as interaction terms with diet group independently, using likelihood ratio tests comparing regression models with and without interaction terms to test for effect modification.

To investigate the role of diet quality as a potential effect modifier, participants will be dichotomised into higher and lower AHEI adherence groups at the median AHEI score in the overall sample to maximise power in each diet group sub-strata. We will also assess the interaction between diet groups and a five-unit increase in AHEI score on hip fracture risk. Other potential effect modifiers include age (continuous and split at < 60 years, ≥ 60 years), sex (male, female), and BMI (continuous and split at < 18.5, 18.5-24.9, and ≥ 25 kg/m² if there is enough power).

The adjusted model will also be further stratified by specific single-nucleotide polymorphisms (SNPs) of genes with a plausible relationship with hip fracture risk and diet (PPAR γ , VDR, MTHFR, CYP24A1, CYP27B1, and IGF-1) to explore potential gene-diet interactions.

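### The AHEI scoring table inverts the kJ-to-kcal conversion for trans fat and PUFA; coded as written, both components would be constant across their scoring ranges

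*SAP*

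**What the plan says.** Section 1.2 of the SAP names AHEI adherence as a potential modifier of the association between diet group and hip fracture. Section 8.2 uses the score in two ways. Participants are "dichotomised into higher and lower AHEI adherence groups at the median AHEI score in the overall sample", and the score also enters as a continuous modifier: "We will also assess the interaction between diet groups and a five-unit increase in AHEI score on hip fracture risk".

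Section 11.1.3 defines the score as 11 components worth 0 to 10 points each: "The total possible score ranges from 0-110 points". Two components are percentages of energy that the analyst must derive:

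- **Trans fat:** minimum score at 4% of energy or more, maximum at 0.5% or less. The source units are given as "Trans fat intake (g/day) and total energy intake (kJ/day) have been previously estimated using 24-hour dietary recall data", and the percentage is to be obtained with "conversion rates of 1 kJ = 4.184 kcal and 1 g trans fat = 9 kcal, respectively".
- **PUFA:** minimum score at 2% of energy or less, maximum at 10% or more. The source units are given as "PUFA intake (g/day) and total energy intake (kJ/day) have been previously estimated from 24-hour dietary recall data", and the percentage is to be obtained with "conversion rates of 1 kJ = 4.184 kcal and 1 g PUFA = 9 kcal, respectively".

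No other part of the SAP states the energy conversion.

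**The concern.** The two rows have the relation between the units backwards. A kilocalorie is the larger unit (1 kcal = 4.184 kJ), so energy held in kJ must be divided by 4.184 to give kcal. The table tells the analyst to multiply.

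The error is squared, because the result is wrong by the ratio of multiplying to dividing. It is large enough to push both components past an anchor for the whole range over which they are meant to discriminate. The result could pass unnoticed at the level of the score, since each component would still return a legal value between 0 and 10 and the total would stay within 0 to 110. At stake is the diet-quality modification analysis, both as a median split and per five units.

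**Working it through.** **Inputs.** All are from section 11.1.3 except the energy limits, which are from section 3.1. The relation 1 kcal = 4.184 kJ is a unit definition.

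- Energy in kJ/day; fat in g/day at 9 kcal per g.
- Anchors: trans fat 4% (0 points) and 0.5% (10 points); PUFA 2% (0 points) and 10% (10 points). The maximum of 10 comes from the text, because the table's heading for the maximum column prints 0.
- Energy limits: 500 and 5000 kcal/day.

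**Step 1. The stated figure.** The plan gives 1 kJ = 4.184 kcal. The correct value is 1/4.184 = 0.239 kcal, so the plan's figure does not reproduce.

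**Step 2. Size of the error.** Percentage of energy = 100 × 9 × g / kcal.

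- Correct: kcal = kJ / 4.184.
- As written: kcal = kJ × 4.184.
- Ratio: 4.184² = 17.506, the same at every energy intake.

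Converting the fat energy to kJ with the written rate, instead of converting total energy to kcal, gives the same percentages.

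**Step 3. Effect on the two components.** Linear scoring between anchors is assumed for the correct scores. The as-written scores need no such assumption, because every value lies beyond an anchor.

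| Component | True % energy | Correct score | Computed % as written | Score as written |
|---|---|---|---|---|
| Trans fat | 0.5 | 10 | 0.029 | 10 |
| Trans fat | 2 | 5.71 | 0.114 | 10 |
| Trans fat | 4 | 0 | 0.228 | 10 |
| PUFA | 2 | 0 | 0.114 | 0 |
| PUFA | 6 | 5 | 0.343 | 0 |
| PUFA | 10 | 10 | 0.571 | 0 |

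Trans fat leaves 10 only above a true 0.5 × 17.506 = 8.75% of energy. PUFA leaves 0 only above a true 2 × 17.506 = 35.0%.

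**Step 4. One participant (illustrative intake).** Take 14 g PUFA at 8,700 kJ/day.

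- Correct: 100 × 9 × 14 / (8700 / 4.184) = 6.06%, scoring 10 × (6.06 − 2) / 8 = 5.07.
- As written: 100 × 9 × 14 / (8700 × 4.184) = 0.346%, scoring 0.

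**Step 5. Range of the total.** With PUFA fixed at 0 and trans fat at 10, the total runs from 0 + 10 = 10 to 110 − 10 = 100. This is a practical bound. It assumes that few participants exceed the limits in step 3, and the SAP gives no intake distribution.

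**Step 6. Check against section 3.1.** In kJ the limits are 500 × 4.184 = 2,092 and 5000 × 4.184 = 20,920. Applying the written rate to these gives 8,753 and 87,529 kcal/day, all above the plan's own upper limit of 5000. The written factor is therefore incompatible with the plan's kcal limits. Section 3.1 itself states no conversion, so it contains no error of its own.

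**Step 7. Median split (illustration only).** Misclassification is arccos(r)/π, where r is the correlation between the sum of the nine intact components and the full 11-component sum. Joint normality and equal SDs of 1 for the nine are assumed, with a common correlation ρ.

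| PUFA SD | Trans fat SD | ρ | r | Misclassified |
|---|---|---|---|---|
| 1 | 1 | 0 | 0.905 | 14.0% |
| 1 | 0 | 0 | 0.949 | 10.2% |
| 0.5 | 0 | 0 | 0.986 | 5.3% |
| 0.5 | 0 | 0.2 | 0.996 | 2.9% |

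**The case against.** The strongest reply is that this is a labelling slip with an obvious intention. Both rows give the inputs, the output and the right constant, and only the unit names are swapped. The table also cites a published scoring guideline and a published nutrient calculation, so it need not be the analyst's only reference. The slip is partly self-revealing too: a true 2,000 kcal/day (8,368 kJ) becomes 35,012 kcal, and a PUFA component that is zero for nearly everyone would stand out in a tabulation. The misclassification figures rest on assumed variances and correlations, not on anything in the SAP.

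Much of this stands. Literal coding is not certain and may be unlikely, and the misclassification range is neither an estimate nor a bound. Bounded scores need not be normal, and negative correlations were not tried.

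The reply does not remove the error. The cells are the plan's stated derivation, the inversion appears twice, and nothing in the SAP corrects it. The energy check would catch it only if one converted energy variable served both the exclusions and the score, and the plan does not say so. Nor does it specify a check of the AHEI component distributions.

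**Conclusion.** The conversion is wrong as written in both rows. If coded literally, energy is overstated 17.5-fold, and PUFA is fixed at 0 and trans fat at 10 across their whole scoring ranges. That leaves 2 of 11 components, or 20 of 110 points, without information over those ranges. This result depends only on the table's own anchors and the unit definition.

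The effect on the median split cannot be determined from the SAP. Under the assumptions shown it is about 3–14% of participants in the wrong half. The score would be degraded, not invalid, since nine components are untouched.

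The consequence is confined to the AHEI effect-modification analyses under a secondary objective. AHEI is not among the listed confounders in section 8.1.3 and does not enter the primary Cox model as specified, so the primary hazard ratios are not affected by the score. The error should be corrected, but it does not threaten the main result.

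**What to change.** In the trans fat and PUFA rows of the AHEI table, replace the stated relation with 1 kcal = 4.184 kJ, and give the working form kcal = kJ / 4.184. As a precaution, use the same direction wherever energy held in kJ is compared with the kcal limits in section 3.1. If any code has already been written from the table, check the converted energy values and the distributions of these two components.

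The cost is two corrected table cells. No new analysis is needed and the primary analysis does not change.
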